- NAB Visual Discrimination
- Oral SDMT
- HVLT-R (Trial 4 and Recognition)
- D-KEFS Category Fluency (skip Condition 1-Letter Fluency for this study)
- D-KEFS Fluency Switching

If the CCB could not be performed at Day 0 or Day 3, then no further attempts should occur and the participant is not considered as part of the sub-study.

Virtual visits will be performed, as necessary, using the site's standard of care telemedicine platform.

Early Treatment Period Visit 2 - day 6 (+/- 3 days) – as needed: *This in-clinic visit may be completed virtually at the participant and study partner's request. This visit only needs to be completed if the study participant and study partner required retraining on use of the study device at the Early Treatment Period Visit 1 - day 3.* The participant (with the assistance of the study partner as appropriate) should complete a treatment administration at the study site to demonstrate to study staff an understanding of how to use the study Device. If participants and their study partner meet the criteria specified in the Treatment Administration Verification Form, the participant will then take the study Device home, treat once more for the day, and commence again with twice daily treatments. If participants and their care partners do not meet the criteria specified in the Treatment Administration Verification Form, the participant will **be withdrawn from the study.**

Phone contacts: (Days 14, 28, +/- 3 day)

During phone calls scheduled every 2 weeks, study staff will review concomitant medications, potential adverse events, potential issues impacting Device treatment adherence and any other issues with the study participant (and study partner, as appropriate). Care should be taken to not over-engage or impact feasibility of protocol adherence with reminders or contact outside of the protocol-defined visits/calls.

Interim treatment Visit: (Day 42 +/- 5 days)

The visit activities should be performed per the SOE. Assessments followed by (SP) should be completed by the study care partner only.

- Confirmation of timing of last DRT dose

SHARPEN, V3.0 -- CONFIDENTIAL

Clinician version – not for patient use

- MoCA v8.2 (on-state)

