- MDS-UPDRS III - clinician-scored motor exam *+Of note, the collection of MDS-UPDRS Part III data should occur in the on-state. The timing of the administration of the MDS-UPDRS Part III from dose should be recorded and kept consistent at each administration of the assessment for that participant.*
- MDS- UPDRS I - patient and caregiver in equal proportion
- MDS-UPDRS II - patient and caregiver in equal proportion
- NPI-Q *(SP)*
- ZBI *(SP)*
- S&E
- Ear Exam
- Concomitant medication and adverse event review

Phone contacts: (Days 56, and 70 +/- 3 day)

The study staff should continue phone calls scheduled every 2 weeks to review concomitant medications, potential adverse events, potential issues impacting Device treatment adherence and any other issues with the study participant (and study partner, as appropriate).

End of Treatment Visit or Early Termination Visit: (Day 84 +/- 5 days)

The visit activities should be performed per the SOE in the appendix maximizing the time between administration of the MoCA (to be completed first) and the Customized Cognitive Battery. Assessments followed by (SP) should be completed by the study partner only.

- Confirmation of timing of last DRT dose
- MoCA v8.3 (on-state)
- MDS-UPDRS III - clinician-scored motor exam *+Of note, the collection of MDS-UPDRS Part III data should occur in the on-state. The timing of the administration of the MDS-UPDRS Part III from dose should be recorded and kept consistent at each administration of the assessment for that participant.*
- MDS- UPDRS I - patient and caregiver in equal proportion
- MDS-UPDRS II - patient and caregiver in equal proportion
- PGI-S/PGI-I
- NPI-Q *(SP)*
- ZBI *(SP)*
- S&E
- Device Useability Questionnaires (Study Participant and Study Partner)
- Ear Exam
- Customized Cognitive Battery (Form 2) *-optional sub study. The best practice is to collect this data in the way it was collected at baseline. For instance, if a participant completed the CCB at the Baseline Visit – day 0 they should complete the CCB at the end of treatment visit. If the first CCB was collected at the Early Treatment Period Visit 1 - day 3, the best practice would be to have them return for a separate visit within 5 days of the end of treatment visit, while continuing to treat with the study device. The CCB must be collected at a single study visit. Data collection of the CCB should not occur in Off-state. Tests should be administered in the following order:*

- HVLT-R (Trials 1-3)

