9.6 Data Safety Monitoring – Independent Medical Monitor

[figure not shown]
Patients with Parkinson’s disease dementia represent a vulnerable population. As such, even though the sponsor deems the TNM™ Device to be a non-significant risk for studies in PDD, the study will utilize an Independent Medical Monitor (IMM).

The IMM is a physician with expertise in PD and dementia, who is not involved in the study and has no conflict of interest with the Sponsor, whose primary responsibility is to provide independent safety monitoring in a timely fashion. The IMM may review the research protocol and ongoing study activities with emphasis on data integrity, protocol adherence and study participant safety issues. The IMM’s review will focus on AEs and reasons for losses to follow up, raising any concerns or issues, and recommending to the continuation, modification or conclusion of the trial, while protecting the confidentiality of the trial data and the results of monitoring.

[figure not shown]
10 Statistical Considerations

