2.2. STUDY ENDPOINTS

Primary Endpoints

• Safety will be evaluated by determining whether tvCVS is associated with a worsening of PD signs and symptoms according to The International Parkinson and Movement Disorder Society Unified Parkinson's Disease Rating Scale (MDS-UPDRS) combined measure of Parts I, II, and III (Goetz, Tilley et al. 2008). This endpoint will evaluate the change in the summed score of MDS-UPDRS Parts I, II and III at the end of the treatment period (day 84), which is defined based on the change relative to baseline (day 0) score.

Adverse events will also be monitored.

- Feasibility will be defined by evaluating both retention rate and treatment adherence rate. Specifically,
 - Retention rate will be defined by the percentage of participants that complete assessments required for analysis of the secondary endpoint:
 - High retention: >90%
 - Moderate retention: 60-90%
 - Low retention: < 60%
 - Treatment adherence rate for each participant will be defined as the percentage of twice-daily treatments with the neuromodulation device completed during the 12-week treatment period:
 - High adherence: >84%
 - Moderate adherence: 55-84%
 - Low adherence: < 55%

Secondary endpoint: The secondary endpoint will evaluate change in the Montreal Cognitive Assessment (MoCA).

Exploratory endpoints: The following outcome measures will be used:

- The Zarit Burden Interview of Caregivers (ZBI)
- The Patient Global Impression of Improvement (PGI-I)
- The Neuropsychiatric Inventory Questionnaire (NPI-Q)
- The Modified Schwab and England Activities of Daily Living Scale (S & E)
- A customized cognitive battery (CCB) which will assess the following functions:
 - Memory
 - Hopkins Verbal Learning Test-Revised (total learning)
 - Hopkins Verbal Learning Test-Revised (delayed recall)
 - Hopkins Verbal Learning Test-Revised (recognition discrimination)
 - o Visuospatial
 - Neuropsychological Assessment Battery Visual Discrimination
 - o Language
 - Delis-Kaplan Executive Function System Semantic Fluency
 - Attention
 - Neuropsychological Assessment Battery Digits Forward
 - Hopkins Verbal Learning Test-Revised (Trial 1)
 - Processing speed
 - Oral Symbol Digit Modality
 - Executive Function
 - Delis-Kaplan Executive Function System Semantic Fluency Switching
 - Neuropsychological Assessment Battery Digits Backward

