6.6.1 PRIMARY ENDPOINTS

(Safety) MDS-UPDRS Parts I, II & III summed score: Changes will be considered to be clinically meaningful worsening if the median difference meets or exceeds the previously established MCID (+5.2 points for clinical worsening) (Makkos, Kovacs et al. 2018). Two-sided, 90% confidence intervals for the combined MDS-UPDRS Parts I, II, and III scores at baseline and the end of treatment period will be constructed. If the median difference (baseline- end of treatment) is less than 5.2 and the confidence interval of the difference (baseline – end of treatment) contains 5.2, then the no clinically meaningful worsening.

(Feasibility)

- **Retention rate** will be defined by the percentage of participants that complete assessments required for analysis of the secondary endpoint:
 - High retention: >90%
 - Moderate retention: 60-90 %
 - Low retention: < 60 %
- **Treatment adherence** rate for each participant will be defined as the percentage of twice-daily treatments with the neuromodulation device completed during the 12-week treatment period:
 - High adherence: >84%
 - Moderate adherence: 55-84 %
 - Low adherence: < 55 %
 - Treatment adherence is captured by the study device and will be reported summarized with minimum, 1Q, median, 3Q, and maximum values. Treatment adherence of \geq 70% is required for inclusion in the Per Protocol cohort.

Adverse Events (AEs): Participants will be assessed for AEs every two weeks at minimum (either at study visits or during phone calls). For each group, the AEs will be summarized with frequency and percentage by preferred (PT) term, with all participants in that treatment group as the denominator. Classification will utilize MedDRA System Organ

Class (SOC) based on MedDRA® Version 26.0 or other terminology/classification common to Parkinson's disease (e.g., falls, freezing of gait, etc.). AE incidence will be summarized by both severity and causal relationship to Device treatment (as determined by the blinded Principal Investigator or designated study personnel). AEs deemed to be of "possible" or "probable" relationship or "related" to the Device will also be considered as device related. Additionally, the number of events and number of device-related events per person will be reported as a distribution.

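### The MDS-UPDRS, MoCA and three other scales are repeated at Day 42, but no analysis or numeric trigger stated in the protocol or SAP uses the scores, so a worsening at week 6 that eases by week 12 would not show in the scored safety result

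*SAP*

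**What the plan says.** **Collected.** Protocol 5.1.1 lists an "Interim treatment Visit: (Day 42 +/- 5 days". Its assessments include "MoCA v8.2 (on-state", "MDS- UPDRS I - patient and caregiver in equal proportion", Parts II and III of the same scale, NPI-Q, ZBI and S&E. The Schedule of Events marks the same items. The visit also includes "Concomitant medication and adverse event review". PGI-S, PGI-I and the optional cognitive battery are not repeated at Day 42.

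**Analysed.** SAP 2.2 takes the primary safety change "at the end of the treatment period (day 84), which is defined based on the change relative to baseline (day 0) score". SAP 6.6.1 states that two-sided 90% intervals for the combined "scores at baseline and the end of treatment period will be constructed", and compares the median difference with a threshold of plus "5.2 points for clinical worsening". SAP 6.5 specifies paired pre/post tests. The MoCA change runs from baseline to end of treatment (Protocol 4.2.2) or to end of treatment or early termination (SAP 6.6.2). Protocol 4.3.2 sets the exploratory changes at Day 84 unless it says otherwise, and it names no Day 42 exception. Neither document contains a by-visit table, a repeated-measures model or a worst-change summary.

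**Monitored.** Protocol 9.6 says that the Independent Medical Monitor's (IMM's) "review will focus on AEs and reasons for losses to follow up". The same section and SAP 5 also give the IMM a wider remit over data integrity and participant safety. The only numeric trigger is in SAP 5: enrollment pauses after two or more SADEs or UADEs.

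**The concern.** The primary safety question is whether tvCVS is associated with worsening of PD signs and symptoms. The trial takes two on-treatment measurements of the score chosen to answer it, and the plan analyses one. A conclusion of no clinically meaningful worsening would therefore take no account of the other.

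If the group worsened past the MCID at week 6 and recovered by week 12, the scored result would not show it. Day 42 is also the only scheduled point that shows the course of the score between baseline and Day 84. In an open single-arm study, any Day 42 analysis not specified beforehand would be chosen after the data had been seen, so the sponsor could not easily defend either reporting it or leaving it out.

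**Working it through.** **1. Is there any stated use of the Day 42 scores?**

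| Place | Visits or data used | Day 42 score used? |
|---|---|---|
| SAP 2.2 and 6.6.1 (MDS-UPDRS) | Day 0, end of treatment | No |
| SAP 6.5 (tests) | pre, post | No |
| SAP 6.6.2, Protocol 4.2.2 (MoCA) | baseline, end of treatment or early termination | No |
| SAP 6.6.3, Protocol 4.3.2 (NPI-Q, ZBI, S&E) | baseline, end of treatment | No |
| SAP 5 (enrollment pause) | count of SADEs/UADEs | No |
| Protocol 8.1 (pause or stop) | device-related serious event, monitor's judgement | No |
| Protocol 9.6, SAP 5 (IMM review) | AEs and losses; general safety remit | Not named, not excluded |

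**2. How much is unused?** Assuming full attendance, 12 participants × 3 visits = 36 totals, of which 12/36 = 33% fall at Day 42. On treatment, 12 × 2 = 24 totals, and 12/24 = 50% fall at Day 42. These are counts of visits, not measures of bias.

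**3. What SD of change do the documents imply?** None is stated, but each document has a worked example for n = 12. Reading the example as SE = (sample mean − MCID)/z and SD = SE × √12:

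- SAP 4 (6.2 points, 80%, MCID 5.20): (6.2 − 5.20)/0.842 × 3.464 = 4.1. With t on 11 df it is 4.0.
- Protocol 10.1 (12.9 points, 90%, MCID 6.70): (12.9 − 6.70)/1.282 × 3.464 = 16.8. With t it is 15.8.

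The two examples differ about fourfold, so SDs of 4 to 16 are used below.

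**4. Illustration of a transient worsening.** These assumptions are not in the documents: normal changes (visit minus baseline, so worsening is positive), within-person correlation 0.5, true change +8 at Day 42 and 0 at Day 84. A flag means a sample median of at least 5.2, so only the threshold part of the SAP 6.6.1 rule is used. There were 100,000 simulated trials per setting, with n = 12 unless stated.

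| SD of change | Flag at Day 84 | Flag at Day 42 | Flag at Day 42 only | Flag at Day 42 only, n = 9 |
|---|---|---|---|---|
| 4 | 0.00 | 0.98 | 0.98 | 0.96 |
| 8 | 0.03 | 0.85 | 0.82 | 0.75 |
| 12 | 0.10 | 0.75 | 0.66 | 0.59 |
| 16 | 0.17 | 0.70 | 0.55 | 0.49 |

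The n = 9 column matches the minimum number of completers in SAP 4.

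**5. Price of treating Day 42 as a second test.** Same settings with n = 12 and no true change at either visit:

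| SD of change | False flag, Day 84 only | False flag, either visit |
|---|---|---|
| 4 | 0.00 | 0.00 |
| 8 | 0.03 | 0.05 |
| 12 | 0.10 | 0.18 |
| 16 | 0.17 | 0.29 |

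At the larger SDs the rise is substantial, which argues for a descriptive summary and against a second decision rule.

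**The case against.** A single end-of-treatment time point is a legitimate choice. Adverse events are monitored under the same primary safety heading, are reviewed at Day 42, are assessed at least every two weeks (SAP 6.6.1) and are tabulated by severity and causal relationship. The go/no-go criteria in Protocol 10.1 and SAP 4 rest on SADEs and completion, so no stated decision turns on an MDS-UPDRS score at any visit. The illustration depends on an assumed pattern of harm. All of this stands, and it limits the point to a missing supportive summary.

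The documents do not support four stronger readings that a reader might infer:

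- *That week-6 worsening would be lost to the trial.* If clinically evident, it can be recorded and reported as an adverse event.
- *That nobody would look at the Day 42 scores.* The IMM has a general safety remit. SAP 5 also describes source review of primary and safety endpoints and at least monthly review of trends, and refers to a Clinical Monitoring Plan and a Data and Safety Management Plan that are not among the documents reviewed. What can be said is that the protocol and SAP state no rule.
- *That an individual would be reported as not having worsened.* The SAP rule concerns a group median and classifies no participant.
- *That Protocol 5.3 predicts transient harm.* It says that the treatment response had not levelled off by 8 weeks. That supports Day 84 as the main time point and gives no reason to expect a worsening that peaks at week 6.

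**Conclusion.** The concern holds as a gap in the prespecified analysis. Half of the scheduled on-treatment MDS-UPDRS totals, and the Day 42 values of MoCA, NPI-Q, ZBI and S&E, have no stated analysis or numeric trigger. This rests on reading the two documents and needs no assumption.

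How much a transient worsening would be missed cannot be settled from the documents. With an assumed +8 points at Day 42 and 0 at Day 84, the Day 84 threshold would pick it up with probability 0.00 to 0.17, against 0.98 to 0.70 for the same threshold at Day 42. Nothing in either document says that this pattern is likely. The case for change is that a summary of data already collected costs almost nothing and gives a fuller answer to the trial's own safety question.

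**What to change.** Reconcile two matters first, because any Day 42 summary would inherit them. The MCID is 5.2 in SAP 4 and 6.6.1 but 6.70 in Protocol 10.1. SAP 6.6.1 also subtracts end of treatment from baseline, which makes worsening negative, yet compares it with a positive worsening threshold.

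Then, in SAP 6.6.1, keep Day 84 as the sole primary time point and decision rule, and add these prespecified supportive summaries beside the Day 84 result:

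- the Day 42 median change in MDS-UPDRS I+II+III with a two-sided 90% CI, using the interval method chosen for Day 84;
- the number and percentage of participants whose worsening reaches the reconciled MCID at Day 42, at Day 84 and at either visit, with denominators stated.

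Give descriptive Day 42 changes for MoCA, NPI-Q, ZBI and S&E. Label all of these as descriptive.

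The cost is a few SAP sentences and table rows, with no new data. The downside is that Day 42 may be read as a second test. Under the assumed SDs, flagging at either visit would raise chance flags from 0.10 to 0.18 (SD 12) or from 0.17 to 0.29 (SD 16), which is why the label matters.

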3. TREATMENT

The study is single arm with all study participants receiving time-varying caloric vestibular stimulation treatments.

4. SAMPLE SIZE DETERMINATION

An enrollment number of 12 was set ensure adequate evaluation of the safety and the feasibility of the study design. Based on the Go/No Go Decision criteria for a follow-on Phase II randomized controlled trial (RCT) in PDD, this Phase I study would need to demonstrate that there were no Serious Adverse Device Effects (SADEs) and that at least 75% of the participants complete assessments required for analysis of the secondary endpoint. This second criterion would mean that at least 9 participants complete the MoCA at the end-of-treatment visit without any SADEs. Utilizing a Poisson distribution, fulfilling these two criteria would yield 95% probability that the true probability of a serious adverse event among the PDD population would be less than 0.33. If all 12 participants completed the MoCA at the end-of-treatment visit without any SADEs, then the study would yield 95% probability that the true probability of a SADEs among the PDD population would be less than 0.25. This relationship is depicted in the following figure:

The likelihood of the population mean being at least that of the outcome's MCID can be determined as a function of the average change in MDS-UPDRS Total score among the sample. The figure below depicts the relationship between the sample (n=12) mean change in MDS-UPDRS Total Score and the likelihood that the true population mean change is 5.20 points (MCID).

To illustrate the usefulness of the above figure, if the average change in MDS-UPDRS Total Score (i.e., the combined measure of Parts I, II and III) among the sample is 6.2 points, then there would be a 80% likelihood that the true population mean change is 5.20 points (i.e., the MCID value) indicating a clinically meaningful worsening of Parkinson's disease signs and symptoms.

5. INDEPENDENT DATA MONITORING

The TNM[™] Device has been designated as a Non-Significant Risk Device for this study. However, the Sponsor has chosen to implement an Independent Medical Monitor (IMM) for the trial to provide independent safety monitoring and to confirm data integrity. The IMM is a physician with extensive experience in Parkinson's disease dementia and clinical trials and has no perceived or real conflict of interest with the Sponsor or in the study outcomes. The IMM will review the research protocol and ongoing study activities with emphasis on data integrity, protocol adherence and study participant safety issues while making recommendations to the continuation, modification or conclusion of the trial. The IMM will review data at least four times per year during the course of the RCT.

In addition to the IMM, the Sponsor will ensure critical safety and data points will be monitored per the SHARPEN Clinical Monitoring Plan (CMP) and the SHARPEN Data and Safety Management Plan (DSMP). A summary of key monitoring procedures is noted below:

Each site will be assigned a Clinical Research Associate (CRA) who will monitor the data to ensure the protection of rights and safety of human subjects, to verify the reported trial data are accurate, complete, and verifiable from source documents, and that the trial is conducted in compliance with the currently approved protocol/amendment(s), with Good Clinical Practice and with the applicable regulatory requirements. For all enrolled study participants, 100% source data review (SDR) and source data verification (SDV), where applicable, will occur of informed consent documents and process, inclusion and exclusion criteria, primary and secondary endpoints, all protocol deviations and safety reports, including adverse events and safety endpoints. Targeted source data verification will occur for all other endpoints and clinical data collected per the Targeted Source Data Verification (TSDV) portion of the CMP. Review of study-wide trends and key risk indicators metrics will be reviewed in a departmental meeting to occur at least once a month. If trends are identified, the Sponsor will review with the study-assigned medical monitor and may implement a Correction and Preventative Action (CAPA) Plan, as necessary. The studyspecific Medical and Safety monitor, who has extensive experience with the device, will review and sign off on all adverse events (AEs) at least monthly, and all Unanticipated Adverse Device Effects (UADEs) within 2 days of acknowledgment of the event. All UADEs will be reported to the ethics committees and all site Investigators per the protocol and regulatory requirements.

No Serious Adverse Device Effects (SADEs) or UADEs are anticipated for this study, if two or more serious and related adverse events (SADE or UADE) are reported, the study enrollment will pause while universality and unblinded review occurs by the Medical and Safety monitor. Additionally, the IMM will review these events for adjudication and agreement and will provide recommendations to the Sponsor.

